10.2 Economic Analyses

Data regarding health utilization, costs, and quality of care will be collected through clinic chart reviews and questionnaires. Data on direct medical costs [inpatient, outpatient, prescription medication, and diagnostic services] will be collected, primarily using chart reviews [health service utilization] and pharmacy plus clinic administrative records [unit costs]. Since out-of-pocket health expenditures predominate in India, we will use a questionnaire to capture that data. The questionnaire also captures direct non-medical [value of participant time spent traveling to and attending appointments] and indirect costs [lost productivity associated with illness or premature mortality].

Economic Analyses: Health expenditures and within-trial cost utility of the intervention compared to usual care will be calculated using a health care system perspective as the base-case analysis and societal perspective for secondary analyses. Only direct medical costs in analyses with a health system perspective will be used, while societal perspective analyses will include direct medical and nonmedical, and indirect costs.

To compare health expenditures between the intervention and usual care arms, costs will first be classified as: direct medical costs based on clinic- and pharmacy-reported data for health utilization and unit costs; patient-reported direct nonmedical costs; patient-reported indirect costs; and costs of the intervention from the clinic and study expenditures [e.g., labor costs for NCMs, costs for educational materials, and overhead costs (facility, administrative, and technology infrastructure) minus costs attributable only to research activities]. Costs associated with identifying individuals with comorbid depression will be summarized. Incremental costs of intervention [implementation, side-effects of multi-condition care, and medical care associated] will be identified. Since in-patient costs over a 36 month study can vary greatly [outliers = a few random disease events], health expenditures will be estimated in two ways: (1) limited to outpatient costs, and (2) combined inpatient and outpatient costs. Because private and government-

funded clinics are included in the trial, mean expenditures will be reported for the intervention arm relative to usual care participants by site and cumulatively.

To compare the within-trial cost-utility of intervention to usual care, an incremental cost-utility ratio will be calculated [net costs to net utility: $\text{costs}_{\text{intervention}} - \text{costs}_{\text{control}} / \text{utility}_{\text{intervention}} - \text{utility}_{\text{control}}$]. To calculate utility for each arm, 6-monthly health utility and mortality data will be used. The chosen measure of utility is the closest option to a global measure, the quality adjusted life year [QALY] and is calculated as the sum of mean survival time [life years] x utility scores at 6, 12, 18, 24 and 36 months. Twelve, 24 and 36 month costs per QALY will be reported.²⁷

If the trial is successful, we will consider comparing modeled long-term cost-utility of the intervention and usual care using Markov Chain Monte Carlo estimation techniques [controlling for age, gender, baseline risk and disease control].²⁸ This will be compared to reference points from the literature – e.g., ceiling ratios for costs per QALY that are less than three times GDP per capita²⁹⁻³¹ are considered cost-effective [India’s 2011 GDP per capita was \$3,700; threshold: $\leq \$11,100$ per QALY]³². Sensitivity analyses will be used to examine the effects of varying discount rates, costs of the intervention, and effectiveness.

11 Study Coordination

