1.2 Secondary Outcomes

To evaluate global, individual, and economic effects of our multi-condition strategy, we will report a number of secondary outcomes *for each study arm at 12, 24 and 36 months*:

- 1) measures of "common effect," i.e., whether the intervention had a similar beneficial effect on all four main targets (SCL-20, HbA1c, SBP, LDL-c);¹
- 2) proportion of participants achieving all 3 CVD risk factor targets in the two groups;
- 3) mean reductions in four main targets (SCL-20 score; HbA1c; SBP; LDL-c);
- 4) proportion of participants achieving treatment targets or significant reductions in individual outcomes (reduced depressive symptoms [$\geq 50\%$ reduction in SCL-20], glycemic control [HbA1c $\leq 7.0\%$ or $\geq 0.5\%$ reduction], BP control [SBP ≤ 130 mmHg or ≥ 5 mmHg reduction], lipid control [LDL ≤ 100 mg/dl or ≥ 10 mg/dl reduction]);
- 5) mean utility, quality of life, and participant treatment satisfaction scores; and
- 6) mean health expenditures and within-trial cost-utility.

2 Background

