6.1 Schedule of Evaluations

VISIT 1–PHQ-9 Screening; Eligibility Screening and Baseline Randomization; 6-monthly Visits for All

Table 4: Schedule of Evaluations

PHASE	Screening	Eligibility testing & baseline (0 month study visit)	Intermediate visits (Intervention Grp)	6-monthly study visits	Sustained effectiveness visits
MONTH	Max -4 weeks	-4 to 0 weeks		6, 12, 18	24 and 36 month visits
Verbal consent	X	X			
Signed informed consent		X			
PHQ-9	X	X	X	X	X
SCL-20		X		X	X
Assess Eligibility + Enrollment	X	X			
Demographics (age, sex, socioeconomic status)		X			
Medical history	X (basic)	X (full)	X (interval)	X (interval)	X (interval)
Family history		X			
Social History (lifestyle/habits)		X	As needed	X	X
Questions regarding Bipolar Disease / Psychosis		X		X	X
Anxiety (GAD-7)		X		X	X
Alcohol use (AUDIT-10) and drug use (DAST-10)		X			X
Cognitive function (MoCA)		X			X
Self-care (SDSCA)		X		X (partial)	X
Quality of Life(HUI-3)		X			X
Diabetes Treatment Satisfaction (DTSQ)		X			X
Costs of Care (records, questionnaire)		X			X
*Acceptability: physician interviews		Likely			Likely
Blood pressure (BP) and heart rate	X	X	As needed	X	X
Height, Weight, BMI (calculated), Waist Circumference		X	As needed	X	X
General Physical Examination		X	As needed	X	X
Eye Examination		X	As needed	As needed	X
Foot Examination		X	As needed	As needed	X
ECG		X	As needed	As needed	X
Urine Microalbuminuria		X			X
Albumin:creatinine ratio (urine analysis)		X			X
†Serum Creatinine Serum Sodium, Potassium and ALT		X	As needed		X
Venous fasting blood glucose (FBG)		X	As needed	X	X
Glycated hemoglobin A1c		X	As needed	X	X
Lipids (TC, HDL, LDL [calculated], TG)		X	As needed	X	X
Glucose-lowering, blood-pressure lowering, and cholesterol-lowering medications		X	As needed	X	X
Other concomitant medications		X	As needed	X	X
Tobacco use		X	As needed	X	X
AE/ SAE Intake (ongoing)			X	X	X

*Qualitative interviews of physician sub-samples will be administered by Coordinating Center staff.

†Follow-up serum potassium and creatinine levels if high and started on ACE-i; follow-up ALT if started on statin.

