6.2.2 Follow-up Study Visits (0, 6, 12, 18, 24, and 36 months post-randomization)

All participants (intervention and control) will be invited to present for the 6-monthly follow-up visits. All participants will have to obtain all investigations: venous FBG, HbA1c, lipid profile, serum creatinine, and other blood biochemistries if necessary, SCL-20, and any complication screenings deemed necessary (urine albumin:creatinine ratio, eye exam, and ECG) prior to the visit. All participants will be required to present the lab results at the visit, if the site does not have a system in place to obtain the laboratory results independently. Participants will be contacted by a study coordinator or the outcomes assessor and scheduled for a full assessment and blood draws.

The outcomes assessor will obtain the following data from the participants:

- Interval history, hypoglycemic events, any adverse events or serious adverse events, other complications developing or changes experienced
- Measures: Blood pressure and heart rate, height, weight, BMI (calculated), waist circumference
- Investigations: values from lab reports; reports of ECG, eye and/or foot exams
- Social/lifestyle habits and questionnaires: self-care (SDSCA), health utilities (HUI-3), diabetes treatment satisfaction (DTSQ), and frequency/costs of care
- SCL-20 and PHQ-9 depression questionnaires
- GAD-7 anxiety questionnaire
- Questionnaires to exclude other psychiatric illnesses (e.g., bipolar disorder, psychosis, reduced cognitive function)

Scheduling:

Follow-up of participants after they have stopped participation in the intervention will be conducted and will include monitoring and reporting any adverse experiences or outcomes. Potential reasons for early termination of study participation can be found in Section 9.7: [Non-Compliance](#)

Non-compliance is the failure to follow national, state, or local regulations governing human subject research, institutional policies related to human subject research, or the requirements or determinations of the IRB. This may pertain to the principal investigator, research staff, or any member or component of the human research protection program.

Examples of non-compliance:

- Performing human subject research without first obtaining ethics committee approval or an ethics committee declaration of exemption
- Deviating from or violating the provisions of an ethics committee-approved protocol

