7.3 Participant Burden

The initial screening questionnaire will require 5 minutes of explanation and opportunity for questions and 10 minutes to complete the PHQ-9 questionnaire, while the travel time to the clinic will vary by distance to the clinic. The more detailed screening assessment to identify reasons that would make a participant ineligible will take approximately 60 minutes to complete. This baseline assessment visit requires traveling to the clinic and undergoing detailed explanation and documentation of informed consent, detailed medical history, clinical examination, anthropometric measurements, and collection of biochemical specimens. All participants enrolled in the trial (whether enrolled in the intervention arm or usual care arm) will also be requested to return to the clinic for follow-up assessments at 6, 12, 18, 24 and 36 months and unscheduled visits are recommended if the participants are not well or it is deemed necessary by the usual care physicians or the case review specialists (these “interim” visits will be shorter than the baseline visit and will be completed by the CC for intervention arm participants and the usual care physician for control participants – documentation in the DS-EHR is required for intervention arm participants, but not control arm participants). At full six-monthly visits, the outcomes assessor will administer detailed questionnaires regarding medical history, self-care activities, depressive symptoms, quality of life, satisfaction, and costs of care, in addition to clinical examination and biochemical measures collected at the clinic laboratory (Table 4). Each visit will require travel to the clinic and approximately 30 minutes to complete questionnaires and 15 minutes to complete the laboratory sample collection. The study will pay all costs associated with these 5 visits (0 (baseline) plus 6, 12, 18, 24 and 36 month time-points) for all participants (intervention arm and usual care), including consultation fee for nurses and research staff, and all measurement tools and laboratory costs. Participants will be provided with 200 rupees to cover their travel and refreshment expenses per visit.

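### Table 4 schedules no HUI-3, DTSQ or cost collection at 6, 12 and 18 months, although other sections collect all three then and need them at 12 months; the QALY formula omits baseline utility and gives no interval rule.

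*Combined protocol and SAP*

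**What the plan says.** **Schedule.** Section 6.1, Table 4 has two scheduled follow-up columns: one for months 6, 12 and 18, and one for months 24 and 36. The HUI-3, DTSQ and costs-of-care rows are marked at baseline and in the second column only.

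Section 6.2.2, whose heading covers every visit from 0 to 36 months, lists "health utilities (HUI-3), diabetes treatment satisfaction (DTSQ), and frequency/costs of care" among the data the assessor obtains. Section 7.3 says that at the full six-monthly visits the assessor gives "detailed questionnaires regarding medical history, self-care activities, depressive symptoms, quality of life, satisfaction, and costs of care", and it points to Table 4 for that content.

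**Use.** Section 1.2 reports secondary outcomes, including utility, satisfaction, expenditure and cost-utility, "for each study arm at 12, 24 and 36 months". Section 10.2 states: "To calculate utility for each arm, 6-monthly health utility and mortality data will be used". It says the QALY "is calculated as the sum of mean survival time [life years] x utility scores at 6, 12, 18, 24 and 36 months" and promises cost per QALY at 12, 24 and 36 months.

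**Adjustment.** Section 10.1 adjusts all primary and secondary treatment effects for baseline characteristics without naming them. Section 10.2 defines the cost-utility ratio from arm-level costs and utilities and does not say whether that adjustment carries over.

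**The concern.** There are three linked problems.

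1. **Schedule conflict.** The visit schedule contradicts the text and the analysis. If a site follows Table 4, HUI-3 and DTSQ scores at 6, 12 and 18 months are never taken and cannot be recovered later. The questionnaire-based costs at 12 months (out-of-pocket, direct non-medical and indirect) are exposed too. Direct medical costs drawn from records could still be cut at 12 months.

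2. **Undefined QALY rule.** The formula lists five post-baseline scores, has no month-0 term although baseline HUI-3 is collected, and does not say what utility applies between visits. The last interval is twice as long as the others. The most direct reading credits each score to the whole interval that precedes it, so a gain that builds gradually is counted from the start of the interval. Two analysts could get different QALYs from the same data.

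3. **Baseline utility.** It is not named as a covariate, and it is unclear whether the denominator of the cost-utility ratio is an adjusted difference.

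Cost-utility is a named secondary outcome, and Section 8.1.1 expects it to inform resource allocation and health policy.

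**Working it through.** **Schedule.** Set side by side for months 6, 12 and 18:

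| Place | HUI-3 | DTSQ | Costs |
|---|---|---|---|
| Table 4 | blank | blank | blank |
| Section 6.2.2 | listed | listed | listed |
| Section 7.3 | collected | collected | collected |
| Use stated in 1.2 and 10.2 | 6, 12, 18 | 12 | 12 |

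Neighbouring rows in Table 4 do fill this column (SCL-20, GAD-7, and SDSCA as partial), so a shifted cell in the PDF reading is unlikely. On Table 4 alone, 3 of the 5 scores in the QALY formula would not exist, and no post-baseline utility would exist by month 12.

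**Formula.** The documents give no utility or QALY figure, so there is none to reproduce and the gains below are assumed. Assumptions: no deaths and balanced baseline utility. Visits at 0, 6, 12, 18, 24 and 36 months give interval lengths L of 0.5, 0.5, 0.5, 0.5 and 1.0 years. Let u be the between-arm utility gain at each visit.

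- End-of-interval: sum of L_i × u_i
- Trapezoid from month 0: sum of L_i × (u_i + u_{i−1})/2

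For a sustained gain (0, 0.05, 0.05, 0.05, 0.05, 0.05):

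- 12 months, end-of-interval: 0.5×0.05 + 0.5×0.05 = 0.0500
- 12 months, trapezoid: 0.5×0.025 + 0.5×0.05 = 0.0375
- Ratio 0.0500/0.0375 = 1.333. For the same net cost, cost per QALY is 1 − 0.0375/0.0500 = 25% lower.
- 24 months: 0.1000 vs 0.0875, ratio 1.143
- 36 months: 0.1500 vs 0.1375, ratio 1.091

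Excess of the end-of-interval rule over the trapezoid, by path:

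| Gains at 0/6/12/18/24/36 months | 12 mo | 24 mo | 36 mo |
|---|---|---|---|
| Sustained: 0, .05, .05, .05, .05, .05 | 33% | 14% | 9% |
| Half kept: 0, .05, .05, .0375, .025, .025 | 33% | 8% | 6% |
| Faded by month 24: 0, .05, .05, .025, 0, 0 | 33% | 0% | 0% |
| Slow build: 0, .025, .05, .05, .05, .05 | 50% | 17% | 10% |

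The percentages depend on the shape of the path, not on the size of the gain.

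**Which rule is nearer the truth?** Suppose the true gain rises linearly to 0.05 over m months and then holds. The true 12-month gain is 0.05 × (1 − m/24):

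| m | True gain | End-of-interval (0.0500) | Trapezoid (0.0375) |
|---|---|---|---|
| 0 | 0.0500 | 0% | −25% |
| 2 | 0.0458 | +9% | −18% |
| 3 | 0.0438 | +14% | −14% |
| 4 | 0.0417 | +20% | −10% |
| 6 | 0.0375 | +33% | 0% |

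The errors are equal at m = 3. The trapezoid is closer when the gain takes longer than 3 months to build.

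**Effect of the missing visits.** For the sustained path, a trapezoid through months 0, 24 and 36 only gives 2×0.025 = 0.050 at 24 months and 0.050 + 0.050 = 0.100 at 36 months. With all visits the values are 0.0875 and 0.1375.

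**The case against.** The schedule conflict is hard to dispute, but its weight and the formula points can be argued.

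- **Section 6.2.2 is partly a pooled list.** It also names items, such as serum creatinine and cognitive-function questionnaires, that Table 4 marks only at baseline and at 24 and 36 months. This stands, but Sections 7.3 and 10.2 carry the point without it.
- **Use at 6 and 18 months is stated only for utility.** This stands. DTSQ and costs have a stated analysis use at 12 months, which is enough for the conflict to matter.
- **Sites may be guided by procedural manuals** (Section 11.1), which are not in these documents. That is possible, but nothing in the protocol says which text governs, and Table 4 is the visit-by-visit schedule.
- **End-of-interval weighting is an inference.** This also stands: what the text shows is an undefined rule, not a deliberate choice of a biased one.
- **The 33% treats the trapezoid as truth.** The ramp table answers this. If the gain builds over 2 to 4 months, neither rule clearly wins. Section 5.2 schedules frequent contact in the first 8 weeks, so a fast build is plausible, though that does not establish the utility path.
- **Baseline adjustment is already promised in general terms, and randomisation leaves only chance imbalance.** This is fair. The third point asks for added precision and is the least important of the three.

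**Conclusion.** The concern holds. Table 4 conflicts with Sections 6.2.2, 7.3, 1.2 and 10.2. If sites follow it, the 12-month utility, satisfaction and cost-per-QALY results cannot be produced.

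The QALY definition is incomplete. Across the four assumed paths, the choice between the two rules moves the incremental QALY by 33% to 50% at 12 months, 0% to 17% at 24 months and 0% to 10% at 36 months. Those sizes rest on assumed utility gains, no deaths, balanced baseline utility and an end-of-interval reading of the formula. The schedule finding rests on none of these assumptions. The matter should be corrected, but it does not touch the primary outcome.

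**What to change.** 1. Mark HUI-3, DTSQ and costs of care in the 6, 12, 18 month column of Table 4, so that it agrees with Sections 6.2.2, 7.3 and 10.2.
2. In Section 10.2, define the QALY per participant as the area under the utility curve by the trapezoid rule from month 0 through 6, 12, 18, 24 and 36 months, with interval lengths 0.5, 0.5, 0.5, 0.5 and 1.0 years and utility 0 from death.
3. Name baseline utility as a covariate for the between-arm QALY difference, and state that the adjusted difference is the denominator of the cost-utility ratio.
4. Report the end-of-interval rule as a sensitivity analysis, because the trapezoid understates a gain that builds in under 3 months.

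The cost is one table correction and a few sentences, presumably with notice to the ethics committees named in Section 4.4. Section 7.3 already counts these questionnaires in the six-monthly visit and its 30-minute estimate, so no burden is added beyond what is described. The 12-month QALY gain may come out smaller.

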11.1 Coordination Plans

The trial has a designated Coordinating Center (at the Madras Diabetes Research Foundation) to oversee the successful design and conduct of the trial. The Steering Committee will support and guide Coordinating Center staff, providing the scientific leadership for the trial. The Executive Committee serves as the operational arm, for day-to-day management, and making any recommendations to the Steering Committee. The Executive Committee will be comprised of the Coordinating Center manager and co-Principal Investigators of the Study.

The Coordinating Center, with input from the Steering Committee, is responsible for developing the protocol; certification of clinic research sites; developing and distributing procedural manuals; training trial personnel in the standardized protocol implementation and data collection; collecting and managing all trial data; quality control; analyzing data; and preparing reports for the Data Safety Monitoring Board, Steering Committee, and NIMH. The Coordinating Center staff will conduct visits to each site to monitor and assure high performance during the trial.

11.2 Laboratories

Central Coordination: The Coordinating Center and laboratory at the Madras Diabetes Research Foundation will coordinate the external quality assurance methods for all clinic research sites.

Clinic Research Site Laboratories: The site laboratories will undergo external quality control checks arranged by the Coordinating Center for cross-site standardization.

11.3 Administrative Clauses

The administrative clauses relating to this protocol are covered by Clinical Trial Agreements (CTA) between the clinic research sites and the Coordinating Center plus the Trial Steering Committee.

Appendix A – PHQ-9 Checklist

PATIENT HEALTH QUESTIONNAIRE-9 (PHQ-9)

Over the last 2 weeks, how often have you had any of the following problems?
(Use "✓" to indicate your answer)

	Not at all	Several days	More than half the number of days	Almost every day
1. Little interest or pleasure in doing things	0	1	2	3
2. Feeling down, depressed, or hopeless	0	1	2	3
3. Trouble falling or staying asleep, or sleeping too much	0	1	2	3
4. Feeling tired or having little energy	0	1	2	3
5. Poor appetite or overeating	0	1	2	3
6. Feeling bad about yourself — or that you are a failure or have let yourself down or your family down	0	1	2	3
7. Trouble concentrating on things, such as reading the newspaper or watching television	0	1	2	3
8. Moving or speaking so slowly that other people could have noticed? Or the opposite — being so fidgety or restless that you have been moving around a lot more than usual	0	1	2	3
9. Thoughts that you would be better off dead or of hurting yourself in some way	0	1	2	3

FOR OFFICE CODING 0 + + +
=Total Score:

If you ticked off any problems, how difficult have these problems made it for you to do your work, take care of things at home, or get along with other people?

Not difficult at all	Somewhat difficult	Very difficult	Extremely difficult
			

‡

‡ Available at: <http://www.lphi.org/LPHIadmin/uploads/.PHQ-9-Review-Kroenke-63754.PDF>.

Appendix B – SCL 20 Questionnaire

SCL-20

Overall, in the past **2 weeks** how much were you distressed by....

		Not at all	A little bit	Mod-erately	Quite a bit	Ex-tremely
1.	Feeling lonely or blue	0	1	2	3	4
2.	Feeling hopeless about the future	0	1	2	3	4
3.	Feeling no interest in things	0	1	2	3	4
4.	Inability to take pleasure in things	0	1	2	3	4
5.	Poor appetite	0	1	2	3	4
6.	Overeating	0	1	2	3	4
7.	Trouble falling asleep	0	1	2	3	4
8.	Awakening in the early morning	0	1	2	3	4
9.	Sleep that is restless or disturbed	0	1	2	3	4
10.	Thinking, speaking and moving at a slower pace	0	1	2	3	4
11.	Feeling so restless you couldn't sit still	0	1	2	3	4
12.	Thoughts of death or dying	0	1	2	3	4
13.	Thoughts of ending your life	0	1	2	3	4
14.	Feeling low in energy or slowed down	0	1	2	3	4
15.	Feeling everything is an effort	0	1	2	3	4
16.	Blaming yourself for things	0	1	2	3	4
17.	Feelings of worthlessness	0	1	2	3	4
18.	Feelings of guilt	0	1	2	3	4
19.	Trouble concentrating	0	1	2	3	4
20.	Difficulty making decisions	0	1	2	3	4

IF Q 13=3 or 4, Invoke self-harm protocol

References

References

2. . !!! INVALID CITATION !!!
3. International Diabetes Federation. Diabetes atlas 5th edition. 2011;2012
